11.2 Power Analysis

Transfusion-naive patients: With a type I error of 5% and a sample size of 60 transfusion-naive patients total (30 PTQA versus 30 historical controls), we will have 85% power to detect changes in the proportion of transfusion-naive patients receiving second transfusion from 100% to 70%.

Transfusion-dependent patients: With a type I error rate of 5% and a sample size of 60 transfusion-dependent patients total (30 PTQA versus 30 historical controls), we will have 83% power to detect a decrease in mean number of units received from 8.0 to 6.5 if the standard deviation is 2.0 units.

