3.2 Inclusion/Exclusion Criteria

Inclusion criteria:

1. Age \geq 18 years of age
2. Patients with MDS, including t-MDS and MDS/MPN
3. Transfusion-naive group: approaching Hb of 8.5 g/dL during enrollment period
 - a. Ideally never-transfused (have never received red cell transfusion)
 - b. If not never-transfused, participants are also eligible for inclusion in this group if they have not been transfused with red cells within last 8 weeks
4. Transfusion-dependent group: Patients with \geq 1 transfusion scheduled during 8-week period prior to enrollment
5. Ability to read and understand English

Exclusion criteria:

1. Age $<$ 18 years
2. Cr $>$ 2
3. Known CHF
4. Unstable Angina
5. Hb level below 7.5 g/dL
6. No plans for potential future outpatient transfusion.

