9.4 Data Collection

Data will be collected via medical record reviews, the QUALMS, and several other survey instruments.

Primary medical record review will include:

- Sociodemographic information
- Information regarding patients' MDS diagnosis, including IPSS-R score
- The number/frequency of transfusions prior to index transfusion (for transfusion-dependent patients)
- Hemoglobin level prior to index transfusion

Secondary medical record review will include:

- The presence of a second transfusion since index transfusion (for those who are starting transfusion)
- The number of red cell units used since index transfusion (for those who are transfusion-dependent)
- The number of hospitalizations since index transfusion
- The number of clinic visits since index transfusion

Survey instruments will include:

- The QUALMS to assess pre- and post-transfusion MDS-related QOL (see Appendix A)
- The Decision Regret Scale, "About Your Care" domain of prior DFCI survey, and the PSS-4 to assess secondary outcomes related to decisional regret, perception of care, and perceived stress (see Appendix B)

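### The 83% power for transfusion-dependent patients is computed correctly but rests wholly on an unsourced SD of 2.0 units, which looks optimistic for this count outcome

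*Protocol*

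**What the plan says.** Section 11.2 (Power Analysis) gives one power figure for this outcome. It assumes "With a type I error rate of 5% and a sample size of 60 transfusion-dependent patients total", split as 30 participants and 30 controls, and puts the power at 83% for "a decrease in mean number of units received from 8.0 to 6.5 if the standard deviation is 2.0 units". It gives no source for the SD, no second value, and no statement of whether the test is one- or two-sided.

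Section 8.1 defines the outcome as the number of red cell units in the 8 weeks after the index transfusion. Section 3.2 admits patients to this group with at least one "transfusion scheduled during 8-week period prior to enrollment". The Epic Workbench description in section 2.2 instead identifies them by more than one transfusion in 8 weeks. Neither place sets an upper limit or a minimum number of units.

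Section 11.1 matches controls 1:1 on transfusion group, IPSS-R, pre-transfusion Hb and institution. Earlier transfusion rate is not a matching factor, although section 9.4 lists this item for chart review: "The number/frequency of transfusions prior to index transfusion (for transfusion-dependent patients)".

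**The concern.** With a mean of 8.0 and an SD of 2.0, about 95% of patients would fall between 4 and 12 units if the distribution were roughly normal. The entry rule allows a wider mix, from patients with one visit in 8 weeks to patients transfused every week. A variance of 4 is also only half the control mean of 8.0, whereas independent single-unit events would give a variance equal to the mean. The SD of 2.0 has to cover both the variation within a patient and all differences between patients.

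This is the only power stated for the primary outcome in this group. If the true spread is larger, the comparison is less sensitive than section 11.2 suggests, and a non-significant result would tell the reader less than the stated 83% implies.

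**Working it through.** **Inputs from section 11.2:** n = 30 per group, difference d = 8.0 − 6.5 = 1.5 units, SD = 2.0, alpha = 5%. Two-sided testing is inferred, because it reproduces the stated figure and one-sided testing does not (89.6% by z, 89.0% by t).

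**Step 1: reproduce the plan's figure.** The standardised difference is d / (SD × √(2/n)) = 1.5 / (2.0 × √(2/30)) = 1.5 / 0.516 = 2.905. By the normal formula, power = Φ(2.905 − 1.960) = Φ(0.945) = 82.8%. By the noncentral t with 58 degrees of freedom it is 81.5%. The stated 83% is the unpaired two-sided normal figure.

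**Step 2: a benchmark for the SD.** Poisson SDs are √8.0 = 2.83 and √6.5 = 2.55. Over the two arms, √((8.0 + 6.5)/2) = √7.25 = 2.69.

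**Step 3: how a few low users affect the SD.** Assume that a share p of patients receives 2 units, the rest have SD 2.0, and the overall mean stays at 8. The mean of the rest is m = (8 − 2p)/(1 − p), and the variance is (1 − p) × 4 + p(1 − p)(m − 2)².

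| p | m | variance | SD |
|---|---|---|---|
| 5% | 8.32 | 3.80 + 1.89 = 5.69 | 2.39 |
| 10% | 8.67 | 3.60 + 4.00 = 7.60 | 2.76 |
| 20% | 9.50 | 3.20 + 9.00 = 12.20 | 3.49 |

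The shares are assumptions; the protocol gives no distribution of units.

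**Step 4: power at other SDs** (unpaired two-sided t-test, 30 per group, d = 1.5; every SD above 2.0 is an assumption).

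| SD | standardised difference | power |
|---|---|---|
| 2.0 | 2.90 | 81.5% |
| 2.5 | 2.32 | 63% |
| 2.7 | 2.15 | 56% |
| 3.0 | 1.94 | 48% |
| 3.5 | 1.66 | 37% |
| 4.0 | 1.45 | 30% |

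A simulated t-test on Poisson counts with means 8.0 and 6.5 gave 56%, in line with the row for 2.7.

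**Step 5: what adjustment for earlier use recovers.** If earlier and later use correlate at r, the residual SD is SD × √(1 − r²).

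| SD | r | residual SD | power |
|---|---|---|---|
| 2.7 | 0.5 | 2.34 | 69% |
| 2.7 | 0.6 | 2.16 | 75% |
| 2.7 | 0.7 | 1.93 | 84% |
| 4.0 | 0.6 | 3.20 | 43% |
| 4.0 | 0.7 | 2.86 | 52% |

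The correlations are also assumptions.

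**The case against.** The sponsor can fairly reply that the power statement is correct as written and openly conditional on its SD. That stands: a reader might infer a calculation error, and there is none.

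A reader might also infer that the SD contradicts the eligibility rule. It does not. Section 3.2 sets a minimum number of scheduled transfusions before enrolment and says nothing about the mean or SD of units afterwards. The Workbench rule in section 2.2 is tighter still. The entry rule makes 2.0 look narrow without excluding it.

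Nor is the Poisson value a lower bound. Units given at regular scheduled visits can vary less than Poisson within a patient. That argument does not cover differences between patients, which the SD of 2.0 must also contain.

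The powers in step 4 ignore the 1:1 matching. In a paired t-test at SD 2.7, power is 55% at a within-pair correlation of 0, 64% at 0.2 and 84% at 0.5; at SD 4.0 it runs from 29% to 51% over the same range. High correlation is doubtful because earlier transfusion rate is not matched, and the plan's own 83% is an unpaired figure.

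Finally, this is a pilot with a convenience sample. No decision rule hangs on this comparison, and nothing in the protocol says that a null result would count against PTQA. Choice of covariates may also be left to an analysis plan that is not shown, so the absence of one from the protocol is not itself a fault. Both replies stand and limit the weight of the point.

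**Conclusion.** The point holds as an unsupported and optimistic planning assumption on which the stated power wholly depends. If the SD were 2.5 rather than 2.0, power would be 63%; at 2.7 it would be 56%, and at 3.0 it would be 48%. The figure of 30% belongs to an SD of 4.0, the upper end of an assumed range.

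These powers rest on an unpaired two-sided t-test, the protocol's difference of 1.5 units, and SDs that the documents neither supply nor rule out. It would go too far to say that the true power is 30% to 56%, or that the comparison cannot detect its target: the protocol has no data on the spread of units from which to conclude either.

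**What to change.** 1. In section 11.2, either justify the SD of 2.0 from the 2015–2017 control records, or show power over a range such as 2.0 to 4.0. State the test and its sidedness beside the figures.
2. Adjust the comparison of units for transfusions or units in the 8 weeks before the index transfusion. Section 9.4 already collects number and frequency of earlier transfusions for transfusion-dependent participants, but it states no look-back window and does not mention units. Fix the window and the measure, and abstract the same field for controls. Because the comparison is historical and not randomised, and earlier rate is unmatched, this reduces confounding by earlier transfusion rate as well as residual spread.
3. Reconcile the descriptions of the transfusion-dependent group in sections 2.2 and 3.2, since the expected spread depends on which applies.

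The cost is a less favourable stated power, one covariate in the model and one extra chart field for controls. The sample size does not change.

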11.3 Securing of Data

As mentioned above, data will be stored in a password-protected RedCap database. Participants will be linked to a deidentified study ID to ensure confidentiality. Please see the Data Safety Monitoring Plan (Appendix E) for further detail.

11.4 Quality Control of Data

We will make every effort to collect all QUALMS data from study participants. RAs will call participants to remind them to complete the questionnaire and to either bring it with them to clinic (pre-transfusion) or mail it back to the site (post-transfusion). We have piloted this technique with 3 patients with MDS at DFCI; all complied. If a QUALMS survey is not complete, the site PI will personally contact each participant. Participants that do not complete the pre-transfusion QUALMS despite personal contact by the PI will be regarded as not having enrolled. We will record all reasons for non-enrollment, and account for all approached participants in the reports.

There may be participants who enroll and complete the pre-transfusion QUALMS, but do not complete the post-transfusion QUALMS. In this case, a PTQA report will not be generated. We will attempt to replace participants who do not complete the post-transfusion questionnaire, although this may prove unfeasible during the two-year timeframe of the study. Whether these participants are replaced or not, we will evaluate the outcomes of these participants, as we may find that there is a change in future transfusion decisions simply from drawing attention to QOL through the pre-transfusion QUALMS. If appropriate, sensitivity analyses will be performed among the subset of patients for whom a PTQA report was generated.

It is possible, although rare, for a patient to die within the two-month follow up period; such patients will be included in analyses based on their clinical and utilization outcomes observed before death.

We will record the number of patients who do not complete the two-month follow up surveys (PTQA utilization, decisional regret, perceptions of care, and perceived stress), and compare patient characteristics between those who do and do not complete the two-month follow up surveys.

**PROTOCOL TITLE: A New Paradigm of Transfusion Decision Support for Patients with MDS:
Using Peri-Transfusion Quality of Life Assessments (PTQAs)**

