1.0 Objectives

1.1 Study Aims

The goal of this multi-center study is to determine how to tailor blood transfusion decisions to the quality of life (QOL) changes experienced by individual patients with myelodysplastic syndromes (MDS). We will assess this by piloting a peri-transfusion QOL assessment (PTQA) approach. The PTQA involves administering a QOL questionnaire (see Appendix A) to study participants before and after an upcoming transfusion appointment and comparing QOL scores.

Specific Aim 1

Assess the feasibility of PTQA. We will assess the feasibility of this new paradigm of decision support by determining the enrollment yield as a percentage of all patients approached. We will also assess feasibility by calculating the proportion of enrolled participants who complete both the pre- and post-transfusion the Quality of Life in Myelodysplasia Scale (QUALMS).

Specific Aim 2

Assess the potential usefulness of PTQA in improving clinical and utilization outcomes. We will use medical record review and match our participants to historical controls (matched for transfusion group; IPSS-R; pre-transfusion Hb; and institution) to assess our primary outcomes, which are:

1. The presence of second transfusion after PTQA (for transfusion-naive)
2. The number of red cell units used after PTQA (for transfusion-dependent)
3. The number of hospitalizations after PTQA (for both transfusion groups)
4. The number of clinic visits after PTQA (for both transfusion groups)

Specific Aim 3

Explore the potential impact of PTQA on patient-reported outcomes. At 8 weeks post-transfusion, we will send participants a follow-up questionnaire (see Appendix B) to assess the following secondary outcomes:

1. PTQA utilization
2. Decisional regret
3. Perception of care
4. Perceived stress

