4.0 Study-Wide Number of Subjects

4.1 Accrual Goal

Our study-wide accrual goal is 60 evaluable participants. To reach this accrual goal, we will consent and enroll 90 participants as some participants are not able to complete the protocol due to a variety of reasons (e.g., participant does not end up requiring future transfusions). The 60 evaluable participants will be matched 1:1 to historical controls seen between 2015 and 2017, for a total sample size of 120.

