11.0 Data Management and Confidentiality

11.1 Data Analysis Plan

Feasibility

Feasibility will be characterized by calculating (1) the proportion of enrolled patients out of all patients approached, and (2) the proportion of patients who completed both the pre- and post-transfusion QUALMS surveys out of all enrolled patients. A convenience sample of 60 evaluable patients will be enrolled to the study. To reach this goal, we will enroll 90 participants total, with the expectation that some patients will not be able to complete the study protocol, despite being eligible at the time of consent (e.g., do not end up requiring future transfusions). If the observed survey completion rate is 50% (i.e. 30/60), then this observed rate is consistent, with 95% confidence, with the true survey completion rate being as low as 38% or as high as 62%.

Clinical and Utilization Outcomes

To be assessed for clinical and utilization outcomes, participants must have completed a pre-transfusion QUALMS, received an index transfusion, and completed a post-transfusion QUALMS. Each of the 60 enrolled evaluable patients will be matched 1:1 to historical controls seen between 2015 and 2017, for a matched sample size of 120 patients total. Subjects will be matched for transfusion group, IPSS-R, pre-transfusion Hb, and institution). Comparative analyses will be conducted separately by transfusion group. For the transfusion-naive, the primary outcome will be receipt of second transfusion (yes/no) within two months following the first transfusion. For the transfusion-dependent, the primary outcome will be defined as number of units pRBCs received within two months following the next transfusion.

For both groups, we will also compare the number of hospitalizations and clinic visits two months after index transfusion (Table).

PTQA Utilization and Patient-Reported Outcomes

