19.0 Setting

19.1 Once a potentially eligible subject is identified and upon provider approval, the RA will meet the patient in clinic to initiate the consent discussion. After a patient consents to the study, he/she will be given a copy of the QUALMS and instructed to complete the survey at home on the day before the upcoming transfusion. The RA will meet the participant in clinic when he/she comes in for a scheduled transfusion. At this appointment, the RA will collect the completed pre-transfusion survey and will give the participant a second copy of the QUALMS to take home. The participant will be instructed to complete the survey at home one week post transfusion and return it by mail. Study participants will also receive the follow-up questionnaire by mail to be completed at home.

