22.0 Recruitment Methods

22.1 Recruitment Procedure

Once the RA has identified potential study participants and confirmed eligibility with the patients' provider, potential study participants will be informed of the study at the appointment prior to their first/next transfusion.

- Patients that are nearing first transfusion will be approached at the appointment prior to their first transfusion.
- Patients that are transfusion-dependent will be approached at an upcoming appointment or transfusion.

Study consent will take place during these visits. Potential participants will be given the opportunity to ask questions, opt out of consideration, and take a consent form home to discuss further with their family and/or other clinicians. We will be clear that enrollment does not mean patients are required to forgo future transfusion if the resulting PTQA report indicates an unimproved or worsened QOL post-transfusion.

Once consented, all DF/HCC study participants will be registered in the DFCI OnCore Clinical Trial Management System by the RA as required by DF/HCC SOP REGIST-101.

- 22.2** The source population for this study is patients with MDS that are presenting to clinic for treatment with blood transfusion.
- 22.3** Eligible subjects will be identified using our study-specific Epic Workbench Report (as described above).

22.4 NA

22.5 NA

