All documents, investigative reports, or information relating to the participant are strictly confidential. Whenever reasonably feasible, any participant specific reports (i.e. Pathology Reports, MRI Reports, Operative Reports, etc.) submitted to the Coordinating Center should be de-identified. It is recommended that the assigned protocol case number (as described below) be used

**PROTOCOL TITLE: A New Paradigm of Transfusion Decision Support for Patients with MDS:
Using Peri-Transfusion Quality of Life Assessments (PTQAs)**

for all participant specific documents. Participant initials may be included or retained for cross verification of identification.

DF/HCC Multi-Center Protocol Registration Policy

Participant Registration and Randomization

Each site will be responsible for registering study participants according to their own institutional policies and procedures. The Coordinating Center will only register patients that are consented and enrolled at DFCI in the DF/HCC CTMS.

Although we will not register participants from Participating Institutions in the DF/HCC OnCore system, Participating Institutions will still be required to complete:

- Signed informed consent document
- Completed Eligibility Checklist

Participating Institutions will notify the Coordinating Center about registrations via monthly phone call.

Protocol-specific interventions may begin once the Participating Institution has registered the participant at their specific site.

Eligibility Exceptions

No exceptions to the eligibility requirements for a protocol without DFCI IRB approval will be permitted. All Participating Institutions are required to fully comply with this requirement.

DF/HCC Protocol Case Number

At the time of registration, the following identifiers are required for all subjects: initials, date of birth, gender, race and ethnicity. Once eligibility has been established and the participant successfully registered, the participant is assigned a unique protocol case number.

Case numbers will be assigned consecutively by DFCI as participants are enrolled. Participating Institutions will be responsible for tracking the appropriate case number as participants are enrolled.

Protocol Deviations, Exceptions and Violations

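### Section 11.4 un-enrols consented patients who miss the pre-transfusion QUALMS, so the Aim 1 completion rate omits one of the two failures it should count

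*Protocol*

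**What the plan says.** Protocol section 1.1 (Specific Aim 1) assesses feasibility by enrolment yield among patients approached and by "calculating the proportion of enrolled participants who complete both the pre- and post-transfusion" QUALMS. Section 11.1 repeats the second measure as "the proportion of patients who completed both the pre- and post-transfusion QUALMS surveys out of all enrolled patients".

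Two passages place enrolment at consent, before the first survey:

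- Section 4.1: "To reach this accrual goal, we will consent and enroll 90 participants". The reason given for taking 90 to obtain 60 evaluable is that some will not get through the protocol.
- Section 11.1 likewise puts the expected non-completers inside the 90 enrolled, describing them as unable to finish "despite being eligible at the time of consent".

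Other places agree on the sequence, though they do not define the denominator:

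- Section 19.1: "After a patient consents to the study, he/she will be given a copy of the QUALMS".
- Section 22.1: "Once consented, all DF/HCC study participants will be registered in the DFCI OnCore Clinical Trial Management System".
- Appendix H, for the other sites: "Protocol-specific interventions may begin once the Participating Institution has registered the participant at their specific site".

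Section 11.4 then says: "Participants that do not complete the pre-transfusion QUALMS despite personal contact by the PI will be regarded as not having enrolled". It adds that reasons for non-enrolment will be recorded and that everyone approached will be accounted for. Its next paragraph describes patients who complete the first survey but not the second, and it treats them as having enrolled.

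**The concern.** The completion endpoint has two components, so a patient can fail it by missing the first survey or by missing the second. Section 11.4 keeps the second kind of failure in the denominator and removes the first kind after the fact, on the basis of the outcome being measured. Those patients are booked as non-enrolment instead.

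Both Aim 1 rates then move, in opposite directions. Completion looks better and yield looks worse than the definitions in sections 1.1 and 11.1 imply. Whether patients will fill in a questionnaire before a transfusion is central to whether this approach can work, and that is the failure the rule takes out of the completion rate. Two analysts with the same data could also report different rates, depending on which use of the word enrolled they followed.

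**Working it through.** **The plan's own figure.** Section 11.1 says an observed 30/60 is compatible with a true completion rate of 38% to 62%. The Wilson 95% interval is

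[p + z²/(2n) ± z·√(p(1−p)/n + z²/(4n²))] / (1 + z²/n).

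With p = 0.5, n = 60 and z = 1.96 it gives 37.7% to 62.3%. The stated interval is reproduced and is correct for 30/60.

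**Notation.** A = approached; E = consented, planned 90 (sections 4.1 and 11.1); C = completers of both surveys, taken as the planned 60 evaluable (section 4.1); m = consented patients who miss the pre-transfusion QUALMS despite contact by the PI. The documents do not give m, so it is an assumption here. The 60 of 90 is a planning allowance, used only to give the shift a scale.

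**Effect of the rule.**

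- Completion: C/E becomes C/(E−m), a factor of E/(E−m).
- Yield: E/A becomes (E−m)/A, a factor of (E−m)/E, whatever A is.
- The two factors multiply to 1, so completers over approached, C/A, does not change.

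| m (assumed) | Completion under 11.4 | Wilson 95% CI | Shift (points) | Yield factor |
|---|---|---|---|---|
| 0 | 60/90 = 66.7% | 56.4–75.5% | 0 | 1 |
| 1 | 60/89 = 67.4% | 57.1–76.3% | +0.7 | 0.989 |
| 3 | 60/87 = 69.0% | 58.6–77.7% | +2.3 | 0.967 |
| 5 | 60/85 = 70.6% | 60.2–79.2% | +3.9 | 0.944 |
| 10 | 60/80 = 75.0% | 64.5–83.2% | +8.3 | 0.889 |

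In the plan's own 30/60 example, if 10 of the 30 failures were at the first survey, the rule would report 30/50 = 60% instead of 50%.

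**What the protocol says about m.** Section 11.4 reports that 3 of 3 pilot patients complied. The exact (Clopper-Pearson) 95% interval for 3/3 has lower limit 0.025^(1/3) = 29%, so the pilot suggests a small m but does not bound it. The only loss the protocol names is patients who turn out not to need a transfusion (sections 4.1 and 11.1). Section 11.4 does not say whether the rule covers them; they are not counted in m above.

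**Two separate minor points on the same counts.**

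- Section 23.2 plans to approach 90 and Appendix F 75, while sections 4.1, 7.1 and 11.1 plan to enrol 90. That would need a yield of 90/90 = 100% or 90/75 = 120%.
- The precision illustration uses 60, although completion is defined over all enrolled. The same 50% on 90 (45/90) gives 39.9% to 60.1%, so the stated interval is slightly conservative.

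**The case against.** The strongest reply is that nothing is hidden. Aim 1 is a pair of measures, and a patient removed from completion appears as a shortfall in yield. The rule is stated in advance, and section 11.4 promises to record reasons for non-enrolment and account for everyone approached, so a reader could rebuild the consent-based rate. That is true, and it rules out any charge of concealed attrition. It does not make the reported rate the one that sections 1.1 and 11.1 define.

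Second, m is probably small. The rule applies only after a reminder call, a possible retry at a later transfusion or, in extenuating circumstances, completion in clinic (section 9.2), and then contact by the PI. Even the 8.3 points at m=10 lie within the roughly 9.5-point half-width of the interval for 60/90. This limits the practical weight. The shift is nevertheless systematic, always in the same direction, and not reflected in the interval.

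Third, sections 19.1 and 22.1 and Appendix H concern handing out surveys and registering patients, not the Aim 1 denominator. I accept that they only corroborate. Sections 4.1 and 11.1 carry the contradiction without them.

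Fourth, the precision illustration contains no arithmetic error. That is so; changing its base is a tidy-up.

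**Conclusion.** Wrong as written, at the low end of severity. The direction is certain: whenever at least one consented patient falls under the rule and some patients complete both surveys, completion is overstated and yield understated relative to a consent-based count. The size cannot be fixed from the protocol. On the planned 60 of 90 it runs from 0.7 points at m=1 to 8.3 points at m=10, with m assumed and never-transfused patients left out; if the rule also covered them, the shift would be larger.

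No go/no-go threshold rests on either rate. Aim 2 is unaffected, since section 11.1 already requires both surveys and an index transfusion for those outcomes. What is at stake is a correctly labelled result for the pilot's first aim.

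**What to change.** In section 11.4, delete the sentence that withdraws enrolled status. State that a patient is enrolled at consent, that completion is computed over all consented patients, and that those who were never transfused, missed the pre-transfusion survey or missed the post-transfusion survey are listed separately. The existing commitment to account for all approached patients can stay.

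If the team prefers to keep the rule, report completion on both denominators and label each: all consented, and consented after the section 11.4 exclusion. In that case also say whether the exclusion covers patients who never needed a transfusion.

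As separate housekeeping, reconcile the numbers approached in section 23.2 and Appendix F with the plan to enrol 90, and base the precision illustration on 90 (45/90: 40% to 60%).

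The cost is wording only, with no new data collection. The one downside is a possibly less favourable reported completion rate.

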1.2 Study Hypothesis

We hypothesize that PTQA may help patients with MDS, primarily by decreasing transfusion use and its attendant iron overload. This includes patients who are starting transfusions (may hold off on additional transfusions if QOL does not improve) and the transfusion-dependent (may extend transfusion interval if QOL does not improve).

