8.0 Study Endpoints

8.1 Study Outcomes

Primary Endpoints

Subjects will be compared with historical controls (matched for transfusion group; IPSS-R; pre-transfusion Hb; and institution) seen between 2015 and 2017. For the transfusion-naïve, the primary outcome will be receipt of second transfusion (yes/no) within 8 weeks following the index transfusion. For the transfusion-dependent, the primary outcome will be defined as number of units pRBCs received within 8 weeks following the index transfusion. For both groups, we will also compare the number of hospitalizations and clinic visits during the 8 weeks after index transfusion (Table).

Secondary Endpoints

Secondary endpoints include decisional regret, perceptions of care, and perceived stress by the associated scales at two months post-transfusion (Table 1).

Table. Primary and Secondary Outcomes, Measured at Two Months after PTQA

Primary	Presence of second transfusion after PTQA (for those undergoing first transfusion) Number of red cell units used since PTQA (for transfusion-dependent) Number of hospitalizations since PTQA Number of clinic visits since PTQA
Secondary	Decisional Regret Decision Regret Scale. ³² 5-item scale provides indicator of health care decision regret; will be tailored to measure regret about transfusion decisions. Perceptions of Care “About Your Care” Domain of Prior DFCI Survey. We previously developed ³³ a 6-item domain based on the Consumer Assessment of Healthcare Providers and Systems Survey “health status” “access,” and “communication” domains. ³⁴ Perceived Stress PSS-4. ³⁵⁻³⁷ The PSS-4 was designed for use with patients with at least a junior high school education, and takes 3 minutes to complete. It contains four questions about feelings of control and overall stress, with simple response alternatives.

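### Outcomes counted only up to death in a fixed 8-week window let a death pass for avoided transfusion, in whichever arm it falls

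*Protocol*

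**What the plan says.** Protocol section 11.4 deals with death in one sentence. It expects few deaths ("It is possible, although rare, for a patient to die within the two-month follow up period") and then fixes how they are handled: "such patients will be included in analyses based on their clinical and utilization outcomes observed before death".

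Section 8.1 defines the outcomes that this sentence feeds:
- Transfusion-naive: "receipt of second transfusion (yes/no) within 8 weeks following the index transfusion".
- Transfusion-dependent: "the primary outcome will be defined as number of units pRBCs received within 8 weeks following the index transfusion".
- Both groups: "we will also compare the number of hospitalizations and clinic visits during the 8 weeks after index transfusion".

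Section 11.1 repeats these definitions with a two-month window. Section 1.2 gives the direction that counts as success: PTQA is expected to help "primarily by decreasing transfusion use and its attendant iron overload".

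The protocol gives no denominator of time alive, no outcome that combines transfusion with death, and no comparison of deaths between arms. The one sensitivity analysis in 11.4 concerns whether a PTQA report was generated. Section 8.2 states that there are no safety endpoints.

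On who is analysed, section 11.1 says "participants must have completed a pre-transfusion QUALMS, received an index transfusion, and completed a post-transfusion QUALMS". Section 11.4 nevertheless says that the outcomes of participants without the post-transfusion survey will be evaluated.

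**The concern.** Success means less transfusion, and a patient who has died receives none. A naive patient who dies before a second transfusion enters the numerator of success. A dependent patient who dies halfway through the window enters with about half the expected units, compared directly with patients observed for the whole window.

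The PTQA reports suggest limiting transfusion when quality of life is stable or worse. In this comparison a death should therefore not be able to look like the intended effect. With no planned tabulation of deaths by arm, a reader of the results could not tell avoided transfusion from lost follow-up time. Even when mortality is equal in both arms, truncated counts add variance and cost power.

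**Working it through.** **Inputs.** From section 11.2: 30 PTQA versus 30 controls per transfusion group; type I error 5%; units 8.0 versus 6.5 with SD 2.0; second transfusion 100% versus 70%. The protocol gives no death rate, so all rates below are assumptions. Units are assumed proportional to time alive.

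**The plan's power figures, reproduced (two-sided).**
- Units: z = 1.5 / (2.0 × √(2/30)) − 1.96 = 2.905 − 1.96 = 0.945, power 82.8% (stated 83%). The exact t-test gives 81.5%.
- Second transfusion, pooled z with continuity correction: (0.30 − 1/30 − 1.96 × √(2 × 0.85 × 0.15/30)) / √(0.21/30) = 0.0860/0.0837 = 1.03, power 84.8% (stated 85%).

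The stated powers are not in error. They simply make no allowance for deaths.

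**Effect of one death in an arm of 30.**
- Naive, before a second transfusion: 1/30 = 3.3 points of the planned 30.
- Dependent, at day 28 of 56: 8 × 0.5/30 = 0.13 units of the planned 1.5. At day 7: 8 × (49/56)/30 = 0.23 units.

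**Naive group, no true effect, controls 30/30.** With 1, 3 or 6 PTQA deaths before a second transfusion, the PTQA proportion is 96.7%, 90% or 80%, and Fisher p is 1.00, 0.24 or 0.024.

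**Units, deaths in one arm only.** Expected shift = 8 × death rate × mean fraction of the window lost. At a 10% rate:
- death uniform over days 0-56: 8 × 0.10 × 0.500 = 0.40
- death uniform over days 7-56: 8 × 0.10 × 0.4375 = 0.35
- death uniform over days 14-56: 8 × 0.10 × 0.375 = 0.30

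The two later ranges apply if PTQA patients must survive to the post-transfusion survey.

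**Simulation of units (two-sided t-test, at least 20,000 runs per setting).**

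| Deaths PTQA / control | True effect | Mean shift due to deaths | Rejection rate |
|---|---|---|---|
| 0% / 0% | none | 0 | 5% |
| 1 expected / none | none | −0.13 | 5.5% |
| 10% / 0%, days 0-56 | none | −0.40 | 10% |
| 10% / 0%, days 7-56 | none | −0.35 | 9% |
| 10% / 0%, days 14-56 | none | −0.30 | 8% |
| 0% / 10% | none | +0.40 | 10% (against PTQA) |
| 0% / 0% | 1.5 units | 0 | 82% |
| 3.3% / 3.3% | 1.5 units | about +0.03 | 75% |
| 5% / 5% | 1.5 units | about +0.03 | 73% |
| 0% / 10% | 1.5 units | +0.40 | 48% |

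**Does the repair work?** Dividing total units by total time alive in the same simulations returns a difference within 0.01 of zero when there is no true effect, and about 1.5 units per 8 weeks when the true effect is 1.5, whichever arm has the deaths.

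For the naive outcome, a competing-risk analysis alone changes nothing when follow-up is complete. If 27 of 30 are transfused again and 3 die first, the cumulative incidence at 8 weeks is 27/30 = 90%, the same as the simple proportion. The composite of second transfusion or death gives 30/30.

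**The case against.** Four points can fairly be made against this.

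1. *The sentence fixes inclusion, not the model.* A rate over time alive would also use only what was observed before death, and the SAP might specify one. This stands in part: a clarification of the sentence is enough. But sections 8.1 and 11.1 define the outcomes as a fixed-window yes/no and numbers of events, and 11.2 powers a difference in mean units. Followed as written, the count is truncated.

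2. *Death is expected to be rare.* This stands. The exclusions (Hb below 7.5 g/dL, Cr above 2, known CHF, unstable angina) point the same way. With one or two deaths the distortion is small, and nothing in the protocol supports 10% versus 0% as a forecast.

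3. *The direction is open.* A reader might infer that the rule would turn harm from PTQA into apparent success. The documents do not support that as a prediction. If 11.1 governs, PTQA participants must survive 7 to 14 days to be evaluable. No such condition is stated for controls, so early deaths would fall among controls and bias against PTQA. If 11.4 governs, that asymmetry is less clear.

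4. *Use may rise before death.* A reader might also infer that every Aim 2 outcome moves towards benefit. Hospitalizations and visits are truncated by death but may increase shortly before it, and units may too. A naive patient who is transfused again and then dies still counts as 'yes'.

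**Conclusion.** The point holds in a limited form. The death rule in 11.4, combined with the fixed-window outcomes in 8.1 and 11.1, scores a naive death before a second transfusion as the favourable result and truncates a dependent patient's unit count. The net bias follows the difference in number and timing of deaths between arms, so its sign cannot be stated in advance. For hospitalizations and visits, even the effect of a single death is uncertain.

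The size is modest if deaths are as few as the protocol expects, and becomes material at about 10% or when the arms differ. The more likely cost is power: one expected death per arm already takes the units comparison from about 82% to about 75%. These figures rest on assumed death rates, uniform death times and units proportional to time alive. The change is worth making because it is cheap and because the plan as written would not show the problem.

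**What to change.** Amend the sentence in 11.4 to say the following:

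- Units, hospitalizations and visits are analysed as rates, with log(days alive and observed within 8 weeks) as an offset. Use a robust variance, because the plan's SD of 2.0 implies a variance of 4, against 8 under a Poisson model with mean 8.
- The transfusion-naive yes/no analysis stays. Second transfusion or death within 8 weeks is added as a prespecified sensitivity analysis.
- Deaths, with their timing, are reported by arm and transfusion group.

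Separately, reconcile 11.1 with 11.4 on whether participants without a post-transfusion QUALMS are analysed. Section 9.2 needs the same check, because it defines the index transfusion as one for which both surveys were completed. If those participants are excluded, require historical controls to have survived the same 7 to 14 days after their index transfusion. The offset does not remove that selection.

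Cost: one date field (death or last contact) in the chart review, slightly wider intervals, and no change to enrolment or to patient care.
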